Study Design:	
Eligible subjects meeting the pathological profile will be recruited at the designated site by the study personnel. Following subject consent, the subjects will be evaluated for eligibility based on their health condition and history.
 
The ACR   U.S. kit, in its original packaging, along with the ACR   U.S. smartphone application will be provided to the subject in a simulated home- use environment. All subjects will be provided with a list of tasks to complete, including providing a urine sample and operating the ACR   U.S. device on both an iPhone 11 device and a Google Pixel 3a mobile phone. After completing the test, the lay user will complete a post-test questionnaire. The study observer will also complete a questionnaire to collect information regarding the lay users' use of the ACR   U.S.
 
The device use will be compared with identified risks to determine if the percentage of failures is acceptable. Additionally, measurable usability criteria for specific, critical steps will be evaluated.
 
Following the usability test performed by the lay user, the subjects' urine samples will be tested by the study staff using the URiSCAN Optima Urine Analyzer. These results will be considered as the “true value”.

Data analysis:	
Results from the ACR   U.S. Urine Analysis Test System and the comparator device, the URiSCAN Optima Urine Analyzer, will be presented in tables listing the results in each group and the % exact match (agreement) and the % <math>\pm 1</math> block match.

Study Sponsor:	
Healthy.io Ltd.

Principal Investigators:	
[name] [name], [name],

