### **6.1. Framework:**

- At least 250 patients will be recruited to participate
- Up to 15% of the samples may be spiked urine samples in case of insufficient native samples in certain blocks
- Multiple sites
- 2 mobile phones: iPhone 11 and Google Pixel 3a (per subject)
- 3 strip lots which will be used interchangeably throughout the experiment

**6.2. Population:** The study is a comparative, controlled trial of subjects who will be recruited from a research clinic. The study population will consist of patients with a medical history of diabetes Type I, Type II, Hypertension, kidney disease and other ailments that represent the target population for urine testing or healthy patients. The intention is to recruit subjects with ailments that will cover all test analytes and all concentrations of these analytes. In the case that analytes and concentrations will not be covered by enrolled subjects, the study will be supplemented with spiked urine samples with the missing analytes and concentrations. However, the number of spiked samples will not exceed 15% of the total samples (all bins combined). Lay users will test their own urine with both smartphones and additionally

may be asked to test another spiked sample, that will be provided by the study staff as necessary and in accordance to protocol.

**6.3. Testing Methods:** Subjects will be recruited for the clinical trials based on their ability to provide a urine sample and comfortably complete tasks using a smartphone. Each urine sample should be tested by a lay user on the ACR | U.S. app, and then transferred to a professional user to conduct the test on the Optima device. The professional user will be blinded to the results of the lay user until after they have completed the test using the Optima device.

**6.4. Timing:** Collection of a urine sample is performed by the patient as part of the study flow. Within 15 minutes from the time of patient's test, testing on the comparator analyzer should be done. This is to best simulate the real-case usage of the ACR | U.S. test. The specimen should not be centrifuged or refrigerated in between tests.

**6.5. Analyzers:** Each urine sample will be tested using the iPhone 11 and Google Pixel 3a devices running the ACR | U.S. application. Each test will be compared to the URiSCAN Optima Analyzer, the comparator device.

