  - 2) The subject will be placed in the private room, with restroom accessibility and internet connectivity, to perform the urinalysis test and complete the task list found below. No training, assistance, feedback, or supplemental instructional materials, other than those described, will be provided to participants. The healthcare professional or other site staff will not be allowed to intervene or answer questions from the subjects during testing, although a 1-800 or clinical assistance phone number, which will be provided to the subject in actual use, will be made available to the subject in case contact is attempted by the subject.
  - 3) The room will be prepared with a desk and chair. The ACR | U.S., in its original packaging will be placed on the desk. The device packaging contains the kit components and the user manual. An in-app instructional guide containing the information most critical to safety and effectiveness is also provided in the form of a readable and understandable, visual, and textual guide on the device App. The patient labeling will be in the format intended for distribution to allow for a realistic evaluation of the labeling effectiveness.
  - 4) The subjects will be asked to follow the device user manual and/or the in-app instructional guide and perform the following tasks:
    - Access the ACR | U.S. App on the smartphone. (iPhone 11 or the Google Pixel 3a)
    - Provide a urine sample in the urine receptacle (to the level marked on the cup) that is included in the ACR | U.S. kit.
    - Immerse the urine strip (provided in the ACR | U.S. kit) in the collected urine specimen for one second.
    - Place the urine strip on the designated area on the Color-Board and wait at least 75 seconds, but not more than 180 seconds.
    - Scan the urine strip and Color-Board with the smartphone App.
    - Send the test results to the study clinician using the smartphone App.
    - Subjects will be asked to complete a questionnaire following completion of the tasks.

[figure not shown]
- 5) Subjects will be observed as they complete the tasks by a research staff member. The research staff observer will complete a dedicated post-test questionnaire.

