- 6) Upon completion of the usability study tasks, the subject will provide the urine sample in the device kit urine receptacle to the research staff for further testing. The research staff will perform the urine analysis test using the comparator device, the URiSCAN Optima device. The research staff performing the urine analysis test with the Optima will be blinded to the results of the ACR | U.S. test, until the test with the comparator device is completed.
- 7) Only after the urine has been tested with the Optima, can the subject begin the test with a second kit on the second smartphone device, provided by the operator in the clinic. A new ID number will be given to the second kit, therefore the lab operator will consider this as new urine and will be kept blinded to the urine results.
- 8) The results of the ACR | U.S. and the comparator device (the Optima) will be used for study purposes only and not for diagnostic or therapeutic purposes of patient management. In the case that urinalysis results are required for patient management, urine specimens from the subject will be sent independently to the hospital/clinic laboratory for analysis and only the results of the hospital/clinic urine analysis will be used for patient care and management. The patient will provide only one urine sample for use in both the study and any subsequent clinical urinalysis testing.

- Stage VI – Post-test procedures

Statistical analyses comparing the results from the ACR | U.S. and the Optima will be performed using an appropriate statistical program and methodology.

In compliance with the ICH/GCP guidelines, the investigator/institution will maintain all eSource and all source documents that support the data collected from each patient, as well as all study documents as specified in ICH/GCP Section 8, Essential, Documents for the Conduct of a Clinical Trial, and all study documents as specified by the applicable regulatory requirement(s). The investigator/institution will take measures to prevent accidental or premature destruction of these documents.

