### **9.1. Completion**

A subject will be considered to have completed the study if the urine sample has been tested.

A subject will be considered to have passed the usability test if he/she was able to scan the Color-Board successfully. In addition, in case a subject failed in his/her first try but identified the problem alone and requested a second kit, and then completed the test, the subject will be considered to have passed the usability test.

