## **10.6. Statistical Analysis**

- General Considerations

Statistical analyses will be performed using an appropriate statistical program and methodology.

Baseline demographic and safety analyses will be performed on all enrolled subjects.

- Demographic and Other Baseline Variables

Demographic and baseline condition related characteristics will be tabulated. Continuous variables will be summarized by a mean, standard deviation, minimum, median and maximum, and categorical variables by a count and percentage.

- Disposition of Subjects

The number and percent of subjects who fail to complete the study and the number and percent of subjects who fail to complete the study because of Adverse Events will be presented.

- Efficacy Analysis

The % exact match (agreement) of the ACR | U.S. compared to the comparator device, for the same Albumin-Creatinine Ratio concentration (block) will be calculated. The %  $\pm 1$  block match (agreement) of the ACR | U.S. compared to the comparator device, for the same Albumin-Creatinine Ratio concentration (block) will also be calculated.

- Usability Analysis

The usability of the ACR | U.S. will be determined by evaluating the percentage of study subjects who are able to complete the device-related tasks, including accessing the ACR | U.S. App, providing a urine sample in the urine receptacle, dipping the kit urine strip in the urine specimen, positioning the strip on

the Color-Board and taking a picture using the smartphone App, with minimal attempts to ask for assistance.

Measurable usability criteria for specific, critical steps, such as time-to-completion, number of requests for assistance, numerical ratings, etc., will be evaluated by observer evaluation and user questionnaire responses. Descriptive statistics will be provided for usability criteria.

- Adverse Event

In general, there are no anticipated adverse events in this study; however, if any adverse events do occur they will be recorded and presented in tables.

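### The usability pass is one score per subject although each subject tests on two phones; the plan does not say how the two outcomes combine and reports no pass rate by phone

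*Combined protocol and SAP*

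**What the plan says.** Each subject uses two phones. Section 6.1 lists "2 mobile phones: iPhone 11 and Google Pixel 3a (per subject"), and section 6.5 adds "Each urine sample will be tested using the iPhone 11 and Google Pixel 3a devices running the ACR | U.S. application". In section 7.1, Stage V, step 7, only after the comparator test "can the subject begin the test with a second kit on the second smartphone device"; that kit is supplied by the clinic operator under a new ID number.

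The pass is per subject. Section 9.1 states "A subject will be considered to have passed the usability test if he/she was able to scan the Color-Board successfully". Its next sentence extends the pass to a failed first attempt, "in case a subject failed in his/her first try but identified the problem alone and requested a second kit, and then completed the test".

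The reported measure is also per subject. Section 10.6 determines usability by "evaluating the percentage of study subjects who are able to complete the device-related tasks", and section 8.2 is worded similarly. Neither splits the percentage by phone. Section 8.2 then applies a permissible percentage of failures, referring to a section 11.6.4.

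The sections differ on what the usability test covers. The synopsis (Study Design) includes in the subject's tasks operating the "device on both an iPhone 11 device and a Google Pixel 3a mobile phone". The task list in section 7.1, Stage V, step 4 has the subject open the "App on the smartphone. (iPhone 11 or the Google Pixel 3a"). Step 6 treats the usability tasks as finished before the comparator test, and the second phone comes after that.

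**The concern.** Two outcomes per subject must become one score, and the plan gives no rule for a subject whose two phones disagree. A home user has one phone, so the useful quantity is success on a given supported phone. Section 1.3 names both phones as supported, and usability is the only secondary endpoint. The result is also to be set against a permissible failure percentage and linked to the device risk analysis (section 8.2, steps 4 and 5). If one phone were harder to use than the other, the planned percentage could fail to show it. An undefined rule also leaves the way of combining the runs open until the results are known.

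**Working it through.** **The plan's own figures.** The plan states no expected usability rate and, in the text available, no threshold, so there is no figure to reproduce. The only planning number is at least 250 subjects (section 10.3), justified by earlier studies, a standard and experience rather than by a formula. It is used below only as a multiplier.

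**Step 1: the readings side by side.**

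| First run, second run | Either phone counts | First run only | Both phones required |
|---|---|---|---|
| success, success | pass | pass | pass |
| success, failure | pass | pass | fail |
| failure, success | pass | fail | fail |
| failure, failure | fail | fail | fail |

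- First sentence of 9.1: a subject who succeeds and then fails was able to scan, so is a pass.
- Failure then success meets that sentence too, but the retry sentence makes recovery depend on the subject finding the problem alone and asking for a second kit. The planned second-phone kit is handed over by the operator and does not clearly meet that condition.
- Section 7.1, Stage V, steps 4, 6 and 7 support the first-run reading. The synopsis supports the both-phones reading.

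**Step 2: formulas.** Let qA and qB be the failure probabilities on the two phones, ρ the within-subject correlation, and j the probability of failing on both.

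- j = qA·qB + ρ·√[qA(1−qA)·qB(1−qB)]
- Either-phone pass rate = 1 − j
- Both-phones pass rate = 1 − qA − qB + j
- Expected subjects failing on exactly one phone = 250·(qA + qB − 2j)

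**Step 3: equal failure rates.** Assume qA = qB = 0.10; the documents give no rate or correlation. The square root is 0.10 × 0.90 = 0.09, so j = 0.01 + 0.09ρ.

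| ρ | j | Either phone | Both phones | Fail on exactly one, of 250 |
|---|---|---|---|---|
| 0 | 0.010 | 99.0% | 81.0% | 250 × 0.180 = 45 |
| 0.3 | 0.037 | 96.3% | 83.7% | 250 × 0.126 = 31.5 |
| 0.6 | 0.064 | 93.6% | 86.4% | 250 × 0.072 = 18 |

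The rate on each phone is 90% throughout. First-run scoring would also give 90%, leaving second-run failures uncounted.

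**Step 4: unequal failure rates.** Assume qA = 0.02 and qB = 0.10, so the phones have pass rates of 98% and 90% (Wilson 95% intervals at n = 250: 95.4% to 99.1% and 85.7% to 93.1%). Under independence j = 0.002; j can range from 0 to 0.02.

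- Either phone: 99.8% (range 98.0% to 100%).
- Both phones: 1 − 0.12 + 0.002 = 88.2% (range 88.0% to 90.0%).
- First run only, with no practice effect: 90% to 98% depending on how many start on each phone; (98 + 90)/2 = 94% if evenly split.
- Fail on exactly one phone: 250 × (0.12 − 0.004) = 29 subjects (range 20 to 30).

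The same performance therefore gives 88.2%, 94% or 99.8%, according to the reading. None of these shows one phone at 98% and the other at 90%.

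**The case against.** A reader might infer that section 9.1 sets an at-least-one-of-two rule, that the secondary endpoint therefore overstates lay-user success, and that a phone on which nobody could scan would still be reported as 100% passing. The documents do not support this:

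- No such rule is written. If any later success turned a failure into a pass, the condition in the retry sentence would do nothing.
- On the first-run reading, a later success cannot rescue a first failure, and 100% would need every subject to start on the working phone. On the both-phones reading, subjects who failed on one phone are failures.
- Sections 8.2 and 10.6 report task completion with minimal assistance and do not cite 9.1, so it is not established that the 9.1 pass is the reported percentage.
- A serious phone-specific problem would probably surface elsewhere: observer and user questionnaires (8.2), missing comparisons for that phone (6.5), or the bench study of several phones (2.1).
- The failure rates and correlations are all assumed, and no changed decision is shown.

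These points stand against the inference of a fixed rule and a demonstrated upward bias. They do not supply a rule for combining the two runs or a planned pass rate by phone. The questionnaire material is planned as descriptive or qualitative, with no split by phone.

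**Conclusion.** The point holds as a gap in the definition with consequences for the result, not as proof that usability is overstated. Three readings have some support in the text. Under two of them a failure on one phone can be left out of the percentage; under the third it is counted but not attributed to a phone. No reading gives a rate for each phone. First-run scoring with everyone starting on one phone would give that phone's rate and nothing on the other.

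The gap of 3.6 to 9.0 percentage points (93.6% to 99.0% against 90%) applies only to the either-phone reading, with an assumed 10% failure on each phone and correlation from 0.6 to 0. The actual size is unknown. The change should be made before the data are seen, because the choice of reading can move the reported percentage.

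**What to change.** - In 9.1 and 10.6, score pass or fail for each subject on each phone. Report the percentage passing on the iPhone 11, on the Pixel 3a and on both.
- Show first-run results separately, with the number of subjects who started on each phone, because second runs are by users who have just practised.
- State in 9.1 that the planned second-phone kit is not the second kit requested under the retry rule.
- Apply the permissible-failure criterion in 8.2 to each phone and correct its cross-reference: in the text available, section 11 covers adverse events and has only 11.1 and 11.2.
- Reconcile the synopsis, section 7.1 (Stage V, steps 4, 6 and 7) and section 9.1 on whether the usability test covers one run or two, and say how the 9.1 pass relates to the percentage in 8.2 and 10.6.

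The cost is wording and two or three extra table rows. The second kit already has its own ID, so scan outcomes can be separated; the two IDs must stay linked to the subject for the both-phones rate. The downside is a reported usability percentage that may be lower.

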### **9.2. Withdrawal from the study**

A subject will be withdrawn from the study for any of the following reasons:

1. Patient has identified that he/she cannot provide a sufficient urine sample.
2. Withdrawal of consent.
3. Patient is not compliant with requirements of the study, including inclusion and exclusion criteria.
4. The study is prematurely stopped or halted (e.g. clinical halt).
5. The investigator believes that for safety reasons (e.g. an adverse event) it is in the best interest of the patient to stop the test.

When a patient withdraws before completing the study, the reason for withdrawal will be documented in the CRF.

## 10. STATISTICAL CONSIDERATIONS

---

### 10.1. Study Design and Objectives

- The study is designed as a comparative, controlled, multi-centered trial to evaluate the accuracy and usability performance of ACR | U.S. in the hands of a potential lay user.

### 10.2. Study Endpoints

- Primary Efficacy Endpoint

The primary endpoint of the study is to calculate the exact % match (agreement) and the %  $\pm 1$  block match (agreement) of the ACR | U.S. (tested by the lay user) compared to the URiSCAN Optima device (tested by a healthcare professional), ), for the tested concentrations (blocks).

- Secondary Efficacy Endpoint

The secondary endpoint of the study is to evaluate the ACR | U.S. usability, by potential lay users under actual use conditions (home environment).

### 10.3. Sample Size Estimation

Sample size estimation was determined according to previous method comparison studies performed using other urine analyzers with similar Indications for Use (see *table 1.0*, Performance testing clinical evaluation) and based on the EP9-A2 standard.

Furthermore, based on our experience in a previous, similar study, at least 250 subjects should represent a sufficient sample size to cover all concentrations and determine the agreement between the ACR | U.S. and the URiSCAN Optima.

### 10.4. Subject Tracking

During the subject recruitment, tracking will be performed to evaluate if the data collected covers the entire range of concentrations measured by the device. If the data is insufficient, spiked urine samples will be used to supplement the missing data. The number of spiked samples will not exceed 15% of the total number of samples (all blocks combined).

## **10.5. Data Analysis Sets**

- Efficacy Analysis Set

The Efficacy analysis set will consist of all subjects without major protocol deviations. Protocol deviations will be defined and classified as minor or major.

- Statistical Analysis of Analysis Sets

The Efficacy analysis set will serve as the main analysis set for the method comparison and usability assessments.

## **10.6. Statistical Analysis**

- General Considerations

Statistical analyses will be performed using an appropriate statistical program and methodology.

Baseline demographic and safety analyses will be performed on all enrolled subjects.

- Demographic and Other Baseline Variables

Demographic and baseline condition related characteristics will be tabulated. Continuous variables will be summarized by a mean, standard deviation, minimum, median and maximum, and categorical variables by a count and percentage.

- Disposition of Subjects

The number and percent of subjects who fail to complete the study and the number and percent of subjects who fail to complete the study because of Adverse Events will be presented.

- Efficacy Analysis

The % exact match (agreement) of the ACR | U.S. compared to the comparator device, for the same Albumin-Creatinine Ratio concentration (block) will be calculated. The %  $\pm 1$  block match (agreement) of the ACR | U.S. compared to the comparator device, for the same Albumin-Creatinine Ratio concentration (block) will also be calculated.

- Usability Analysis

The usability of the ACR | U.S. will be determined by evaluating the percentage of study subjects who are able to complete the device-related tasks, including accessing the ACR | U.S. App, providing a urine sample in the urine receptacle, dipping the kit urine strip in the urine specimen, positioning the strip on

the Color-Board and taking a picture using the smartphone App, with minimal attempts to ask for assistance.

Measurable usability criteria for specific, critical steps, such as time-to-completion, number of requests for assistance, numerical ratings, etc., will be evaluated by observer evaluation and user questionnaire responses. Descriptive statistics will be provided for usability criteria.

- Adverse Event

In general, there are no anticipated adverse events in this study; however, if any adverse events do occur they will be recorded and presented in tables.

